### **3 INCLUSION AND EXCLUSION CRITERIA**

#### **3.1 Inclusion Criteria (Main Cohort)**

To be included in this study, participants must meet the following criteria:

- 1 Patients with cancer, with the exception of patients with active acute leukemia and allogeneic hematopoietic stem cell transplant recipients. Patients may be on active therapy or received therapy (e.g., chemotherapy, radiation, or surgery) within 7 years. Patients with active cancer who have not yet been treated (e.g. newly diagnosed cancer or early stage MDS or CLL) are eligible. Basal cell cancer and carcinoma in situ treated with local excision alone do not qualify for inclusion.
- 2 Presence of symptomatic infection, defined by fever ( $T \geq 38.0^{\circ}\text{C}$ ) OR respiratory symptoms (cough, nasal congestion, or shortness of breath), OR lung infiltrates on chest X-ray or CT imaging, Diagnosis of COVID-19 is based on PCR testing of respiratory samples.
- 3 Age equal to  $\geq 18$  years or older (children are excluded because COVID-19 typically has a milder course in children, and lack of safety data of this regimen in children).
- 4 Laboratory evaluation:
  - Platelet  $\geq 75,000/\mu\text{L}$
  - Hemoglobin  $\geq 9 \text{ g/dL}$
  - Hematocrit  $\geq 27\%$
  - Absolute Neutrophil Count (ANC)  $\geq 1000/\mu\text{L}$
  - Creatinine clearance  $\geq 50 \text{ mL/min}$  (Cockcroft-Gault Equation—note: plasma creatine instead of serum is used at Roswell Park)
  - Total bilirubin  $\leq 2 \times$  institutional ULN
  - AST (plasma) and ALT(plasma)  $\leq 2 \times$  institutional ULN
  - Plasma amylase and lipase  $\leq 2 \times$  institutional ULN
- 5 In the absence of COVID-19, a life expectancy of 6 months is expected.
- 6 Participant must understand the investigational nature of this study and sign an Independent Ethics Committee/Institutional Review Board approved written informed consent form prior to receiving any study related procedure.

**NOTE:** For blood chemistry labs, Roswell Park clinical blood chemistries are performed on plasma unless otherwise indicated.

Roswell Park Protocol No.: I-659920

Refer to **Appendix D** for the Investigator Study Eligibility Verification Form (Main Cohort): Inclusion Criteria.

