## 2 BACKGROUND

### 2.1 Enhanced Risk of COVID-19 Mortality and Morbidity in Cancer Patients

Patients with cancer and COVID-19 had a 5-fold higher risk of severe events, defined as ICU admission requiring invasive ventilation or death, than those without cancer (1). Currently, there is no proven effective treatment of COVID-19 beyond supportive care. **This trial is based on the central premise that SARS-coronaviruses persist in host cells and in infected hosts by evasion of the innate antiviral responses mediated by RNases (especially RNase-L/OAS) and type-1 interferon (IFN $\alpha/\beta$ ) pathway and IFN-stimulated genes (ISG), and that early therapeutic activation of this pathway will limit viral replication and expansion in patients' tissues, thus preventing severe complications.** SARS-CoV-2 is related to SARS, MERS, and other coronaviruses, which are positive-sense RNA viruses that generate dsRNA during replication. One of the principal IFN antiviral pathways involves activation of the host RNases, especially RNase L, which is induced directly by dsRNA (predominantly by RIG-I and MDA5 helicases (2)) and indirectly by IFN $\alpha/\beta$ , degradation of viral RNA (3) and amplified IFN $\alpha/\beta$  production (2). Coronaviruses avoid upstream pathways that activate type 1 IFNs by cytosolic pattern recognition receptors (e.g. RIG-I and MDA5) preferentially activated by the coronavirus RNA (2, 4), and inhibition or avoidance of IRF3, a transcriptional factor that mediates the induction of type 1 IFNs, by that pathway (5-9). This inhibition of innate immune responses allows the virus to replicate in

Roswell Park Protocol No.: I-659920

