Our study will enroll patients with cancer with varying comorbidities and levels of COVID-19 severity. For outpatients with COVID-19 at high risk for severe complications based on age and co-morbidities, a monoclonal antibody cocktail (e.g. Regeneron's combination of casirivimab and imdevimab) is standard of care. In patients with more severe COVID-19 who are hospitalized and require supplemental oxygen, therapy is focused on controlling inflammatory injury. Dexamethasone was associated with a survival benefit and will be administered to all patients who meet criteria for this agent. Other anti-inflammatory agents such as IL-6-targeting agents and baricitinib can also be of value, although their benefit when added to corticosteroids is unclear. The antiviral agent, remdesivir, is of unclear value based on conflicting data; at best it shortens the duration of illness but doesn't have a survival benefit. At Roswell, we routinely administer combination dexamethasone and remdesivir to inpatients with significant COVID-19, and will do so for patients enrolled in this protocol unless there is a clinical contraindication to receiving either agent. The data on convalescent plasma is also contradictory, but plasma with high neutralizing titers against the viral Spike protein is likely to be of value. We do not know the effect of these standard of care regimens on nasopharyngeal viral load in patients with cancer. In addition, since these regimens are often administered concurrently, it's difficult to delineate the effect of a specific drug on viral load. Based on our experience at Roswell Park, the nasopharyngeal viral load in some

Roswell Park Protocol No.: I-659920

immunocompromised patients with cancer (e.g. stem cell transplant recipients and patients receiving B-cell-depleting agents), has persisted for several weeks despite receiving combinations of these agents (e.g. remdesivir and dexamethasone, often in combination with convalescent plasma). The standard of care for COVID-19 changes over time. Regarding the current protocol, the study regimen will be added to what in our judgment is the best standard of care regardless of outpatient or inpatient status.

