## 5 LOCAL AND STUDY-WIDE RECRUITMENT METHODS

### 5.1 Recruitment

Subjects will be recruited from Roswell Park and our affiliate practices, and University at Buffalo-affiliated hospital systems. Recruitment efforts will focus on patients with initial signs of COVID-19 who would be offered enrollment as soon as feasible. In addition, asymptomatic patients with contact (e.g., household member or health care-associated exposure) with COVID-19 will be monitored for development of symptoms or signs of COVID-19 that would result in nasopharyngeal swab PCR testing: Roswell Park is a New York State-designated regional laboratory for COVID-19 PCR-based testing with same or next day reporting of results.

Men and women will be recruited, with age, race, and socioeconomic status expected to reflect the general Roswell Park patient population.

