#### **11.4 Nasopharyngeal swabs**

Nasopharyngeal swabs will be taken for viral quantification by quantitative PCR on:

- Screening: If a potential study participant has already been identified as COVID-19-positive from an outside testing facility, as per current institutional protocol, a nasopharyngeal swab will be obtained for quantitative PCR. Study drug therapy will be initiated within 3 days of screening, including on the same day of screening.
- Each day of treatment (Day 1 and Day 3 (+ 1 day)).
- Follow-up Visits on Days 7 and 14

Testing for SARS-CoV-2 will be done upfront and residual samples will be tested for baseline viral load. If there's a problem in supplies, repeat sampling at the indicated time points may not be feasible and will not be considered a protocol deviation.

All samples will be transported to the Molecular Diagnostics facility (Attn: [name]) The screening samples will be tested for SARS-CoV-2 as per current institutional protocol; The residual sample left over from clinical testing, as well as from subsequent testing, will be processed by the Molecular Diagnostics facility and the resulting research analytes will be transported to the [name] laboratory for storage and analysis ([name]).

Any remaining RNA may be also analyzed for the markers of antiviral immunity described in the blood correlative studies.

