### 19.2.2 Efficacy

In order to compare the AUC between rintatolimod versus historical institutional benchmarks we will use the highly efficient approach proposed by Chandrasekhar et al (48). Ct values measured at baseline (Day 0), Days 3, 7 and 14 will be used to measure the AUC using a standard trapezoidal rule where the AUC for the  $i$ th subject in group  $k$  ( $k=1$  for rintatolimod and  $k=2$  for control) as  $AUC_{jk} = \sum_{i=1}^m c_j Y_{ijk}$  where  $t_1 = 0, t_2 = 3, t_3 = 7, t_4 = 14, t_5 = 30$ ,  $m = 5$ , the  $Y_{ijk}$ 's denote the corresponding Ct values per subject at the respective time points and

$$c_j = \begin{cases} \frac{t_{j+1} - t_j}{2}, & j = 1 \\ \frac{t_j - t_{j-1}}{2}, & j = m \\ \frac{t_{j+1} - t_{j-1}}{2}, & \text{otherwise} \end{cases}$$

If a Ct value is  $>40$  it will be considered right censored for the purpose of this analysis, which corresponds to a non-detectable level. We can re-express this formulation using a linear mixed model with details given exactly as in Chandrasekhar et al. (48). A large AUC value for a respective subject is a measure of treatment efficacy as compared to a subject with a lower AUC

Roswell Park Protocol No.: I-659920

value. The primary test of efficacy will be H0:  $AUC=130$  (log2 copies) x day versus H1:  $AUC>130$  (log2 copies) x day.

The secondary clinical efficacy endpoints of (i) progression of infection requiring hospitalization in patients who were not inpatients at study entry; (ii) respiratory failure requiring mechanical ventilation; and (iii) death within 30 days will be compared using Fisher's exact test. Time to a Ct value of non-detectable will be examined using an exact discrete time-to-event Cox model. The analysis of correlative endpoints will be primarily descriptive and graphical in nature.

The primary test of efficacy will be one-sided and tested at level alpha=0.05. All additional tests will be two-sided and tested at level alpha=0.05.

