### **19.3 Sample Size Justification**

The sample size was based on preliminary data gathered at Roswell Park on patients and employees. The values were similar between the two study groups. The Ct values collected at baseline for n=20 patients and employees had an average of 24.1 log2 copies with a standard deviation of 6.5. The standard deviations after baseline was approximately 4.5 as the Ct values increased. The preliminary estimate for the AUC based on our pilot data is 130 (log2 copies) x day, which is the basis for our null hypothesis. The between time point correlation was estimated to be approximately rho=0.3. Given n=10 subjects we will be able to detect and increase in the AUC to an average of 144 (log2 copies) x day (efficacy) or greater than our assumed institutional benchmark of 130 (log2 copies) x day at power=0.80 and alpha=0.05(one-sided). We simplified this calculation assuming no censoring, which will be accounted for in the final analysis and assumed a compound symmetry covariance structure with the correlation estimate described above.

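### The primary Ct AUC test against a fixed benchmark takes no account of time since symptom onset, so a difference in illness stage can mimic or hide a drug effect

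*Combined protocol and SAP*

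**What the plan says.** **Premise and recruitment.** Section 2.1 rests the trial on the idea that "early therapeutic activation of this pathway will limit viral replication and expansion". Section 5.1 adds: "Recruitment efforts will focus on patients with initial signs of COVID-19 who would be offered enrollment as soon as feasible". That is an aim and carries no number of days.

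**Entry.** Item 2 in both cohorts (3.1 and 3.3, repeated in Appendix D) requires "Presence of symptomatic infection, defined by fever", respiratory symptoms or lung infiltrates, with a PCR diagnosis. Neither the criteria nor the forms in Appendices D and E bound the time since onset or since the first positive test. The one timing limit runs from screening to first dose (11.4): "Study drug therapy will be initiated within 3 days of screening, including on the same day of screening". PCR positivity does not bound illness duration either: Section 2.6 reports that viral load in some immunocompromised patients "has persisted for several weeks despite receiving combinations of these agents".

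**Data collection.** A general medical history is taken, but neither Section 11.1 nor the calendars in Appendix F name the date of onset.

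**Analysis.** Section 19.2.2 sets out its AUC method "In order to compare the AUC between rintatolimod versus historical institutional benchmarks". The stated hypothesis is one-sample: AUC = 130 against AUC > 130, on raw Ct, with a larger AUC read as efficacy. Section 19.3 takes the 130 from pilot data on patients and employees and does not give their day of illness.

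**The concern.** With no concurrent control, the test is fair only if the 10 treated patients would have had a mean AUC of 130 without the drug. That depends on where in the illness the clock starts. For treated patients it starts at first dose; for the benchmark subjects the starting point is not described. Section 19.3 says Ct values increased after baseline in the pilot data. A patient who enters later on that rising path scores a higher AUC with no drug effect, and one who enters earlier, or who sheds virus for weeks, scores a lower one. The plan neither limits, records nor adjusts for this, so drug effect and time of enrolment cannot be separated. The result matters beyond this trial, because Section 2.6 presents it as the foundation for a larger randomized trial.

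**Working it through.** **Inputs from Sections 19.2.2 and 19.3.** Null 130; alternative 144 (difference 14); n = 10; one-sided alpha 0.05; power 0.80; baseline Ct 24.1 with SD 6.5; later SD 4.5; correlation 0.3 (compound symmetry). The text names Days 0, 3, 7 and 14; the formula adds Day 30. *Assumption, not in the documents:* Ct rises b = 0.3 to 1.0 per day without the drug.

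**Step 1: the plan's own figure.** Trapezoid weights for Days 0-14 are 1.5, 3.5, 5.5, 3.5 (sum 14). Weight times SD gives 9.75, 15.75, 24.75, 15.75: sum 66.0, sum of squares 1203.75.

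Var(AUC) = 0.7 × 1203.75 + 0.3 × 66.0² = 842.6 + 1306.8 = 2149.4, so SD = 46.4.

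Power for a difference of 14 with n = 10 is then 22% (noncentral t, 9 df), not 80%. The Day 0-30 weights 1.5, 3.5, 5.5, 11.5, 8 (sum 30) give SD 95.7 and power 11%. The level does not fit either: a flat Ct of 24.1 gives 14 × 24.1 = 337 over 14 days, against a null of 130.

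Of the constructions tried, only one reproduces 144 at 80% power: an unweighted sum of five Ct values. Var = 0.7 × 123.25 + 0.3 × 24.5² = 266.4, SD = 16.3, power 80.4%. That is not the trapezoid written in 19.2.2.

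**Step 2: stage gap equal to the target.** If every value sits d days further along a path rising b per day, AUC moves by W × b × d, where W is the sum of the weights. Setting this to 14 gives d = 14 / (W × b).

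| Construction | W | 14 units in Ct | Days at b = 0.3 | b = 0.5 | b = 1.0 |
|---|---|---|---|---|---|
| Day 0-14 trapezoid | 14 | 1.00 | 3.3 | 2.0 | 1.0 |
| Day 0-30 formula | 30 | 0.47 | 1.6 | 0.93 | 0.47 |
| Five-value sum | 5 | 2.80 | 9.3 | 5.6 | 2.8 |

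These figures ignore the limit at Ct 40. A hard cap lengthens some of them. For the five-value sum at b = 1.0, starting from 24.1, Day 30 is already at the cap and Day 14 can rise only from 38.1 to 40. Then 3d + 1.9 = 14, and d = 4.0.

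**Step 3: a slower slope.** If 130 is a five-value sum with baseline 24.1, the later values average (130 − 24.1)/4 = 26.5. Spread over a mean time of (3 + 7 + 14 + 30)/4 = 13.5 days, the slope is (26.475 − 24.1)/13.5 = 0.18 Ct per day. A gap of 1 to 3 days then moves the score by 0.9 to 2.6 units, or 6 to 19% of the target.

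**Step 4: effect on the test, assuming a null correct for the scale.** On the Day 0-14 trapezoid (SD 46.4), a spurious shift of 14 raises the one-sided false-positive rate from 5% to 22%, and a shift of 28 to 55%. A shift of −14 cuts the power for a true +14 to 5%. On the five-value sum (SD 16.3), a shift of 14 gives 80%; at the slope in Step 3, a gap of 1 to 3 days gives about 7 to 12%.

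**The case against.** **Baseline viral load is said to be used.** Sections 2.6 and 19.1 refer to each patient's own baseline. If AUC meant change from baseline, a stage shift would cancel while Ct rises linearly. But 19.2.2 defines AUC on raw Ct and its hypothesis has no baseline term, so this protection is not in the specified test. It is tempting to add that baseline Ct could not help because the same value occurs on the rising and falling limbs of infection. The documents do not show this; 19.3 says only that Ct increased.

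**A reader might infer that 1 to 3 days is established as the whole target effect.** It is not. That figure needs the Day 0-14 trapezoid and an assumed slope, and the plan's own 130 and 144 do not fit that trapezoid.

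**The error rates are not evidence about illness stage.** This stands. They are the power of the test at a given shift, whatever its cause, and they presuppose a corrected null. With SD 46.4, a flat Ct of 24.1 set against 130 gives t of about (337 − 130)/(46.4/√10) = 14, so on that scale the written test would reject almost regardless.

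**The population is less open than it looks.** Section 5.1 aims at initial signs. Allogeneic transplant recipients, who may be among the long-term shedders, are excluded from the Main Cohort. Section 2.2 also gives a rationale for treating more severe disease. This narrows the point. Patients on B-cell-depleting agents, also named in 2.6, remain eligible, and an aim is not a measured variable.

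**Conclusion.** The point holds as a gap in the design of the comparison. Followed exactly, the plan can turn a difference in illness stage between the 10 patients and the benchmark subjects into apparent benefit, or can conceal a real effect. The direction follows from the plan's own statements that Ct rose after baseline and that a higher AUC is better.

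The size is not determined by the documents. Under an assumed 0.3 to 1.0 Ct per day, the gap that equals the 14-unit target runs from about 0.5 to 9.3 days across the three constructions, before any cap at 40; slower slopes need longer. The AUC scale is the prior defect and must be settled before any single figure is quoted. Nor do the documents show that the trial patients will in fact differ in stage from the benchmark: the plan collects nothing that would reveal it. The change is recommended, and it does not depend on restricting entry.

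**What to change.** 1. **Record** the date of first COVID-19 symptom and the date of first positive PCR on the screening form, and abstract both for the historical patients. Where no onset date exists, for example with entry on infiltrates alone, use the first positive PCR date and flag it.
2. **Tabulate** days since onset at first dose by cohort and dose tier, and the corresponding days for the benchmark subjects.
3. **Reconcile** the AUC in 19.2.2 and 19.3: last time point (Day 14 or Day 30), weights, and the origin of 130 and 144.
4. **Then pre-specify** in 19.2.2 either a comparison with patient-level historical data adjusted for days since onset and baseline Ct, or a benchmark re-estimated for the trial's distribution of days since onset. At the least, make this a key supporting analysis on which the efficacy conclusion is conditional.

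No eligibility change is needed. The cost is two dates on a form, the same two in the historical chart abstraction, and a revised analysis section. Some historical patients will lack dates and must be aligned on the first positive test or dropped. With n = 10, and pilot baseline values on only 20 people, the adjusted comparison will be imprecise, and the plan should say so.

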### **Correlative Endpoints**

- Determine the kinetics of changes of the immune subsets and circulating inflammatory mediators (including CRP, cytokines, chemokines, interferons) in peripheral blood in the course of treatment at baseline (Day 0), Days 3, 7, and 14. Plasma and PBMCs will be cryopreserved for future exploratory studies, including the assessment of intracellular signaling and TCR and BCR repertoires as correlates of response to the study regimen.
- Induction of known mediators of antiviral immunity that include (myxovirus resistance gene, MxA; protein Kinase R (PKR); oligoadenylate synthetase-2 (OAS2); RNase-L, IFN-stimulated gene-15 (ISG15); IFN-induced proteins with tetratricopeptide repeats (IFIT1) and IFN-inducible transmembrane protein 3 (IFITM3), TLR3, RIG-I, MDA5, IRF3, IRF7, in nasopharyngeal swabs material and blood cells of patients on all tiers of treatment. Expression of ACE2 (receptor for SARS-CoV-2 entry) and potentially other genes involved in SARS-CoV-2 infection will be tested in nasopharyngeal samples.

Roswell Park Protocol No.: I-659920

All subjects meeting the eligibility criteria who signed a consent form and receive rintatolimod control will be considered evaluable for efficacy analysis. Safety analysis will be performed on all patients who have signed a consent form and received at least one dose of study medication.

The primary efficacy analysis of the Phase IIa component of the study will be on the intention to treat (ITT) population, which will include all patients who have signed a consent form and undergone randomization, according to the treatment group to which they were allocated.

All data collected will be summarized and presented. Continuous variables will be described as the mean, median, standard deviation, and range of the observations. Categorical data will be described with contingency tables including frequency and percentage. Individual patient listings will be generated and presented.

Statistical descriptions and analyses will be carried out using SAS statistical analysis software version 9.4 or higher (SAS Institute, Inc., Cary, North Carolina, USA).

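### The viral-load analyses do not require detectable virus before the first dose, so a patient already non-detectable at baseline counts toward antiviral efficacy

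*Combined protocol and SAP*

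**What the plan says.** **Entry.** Sections 3.1 and 3.3 (item 2 in each) and Appendix D ask for fever, respiratory symptoms or lung infiltrates, and state that "Diagnosis of COVID-19 is based on PCR testing of respiratory samples". None of Sections 3.1-3.4 or Appendices D and E limits the age of the PCR, sets a Ct limit, or requires a positive screening or Day 1 swab.

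**Screening.** Section 11.4 provides a new quantitative swab "If a potential study participant has already been identified as COVID-19-positive from an outside testing facility", but makes nothing depend on its result. It continues: "Study drug therapy will be initiated within 3 days of screening, including on the same day of screening". Section 5.1 describes "same or next day reporting of results", so the first infusion can precede the baseline result.

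**Analysis population.** Section 19.1 (under Correlative Endpoints) says: "All subjects meeting the eligibility criteria who signed a consent form and receive rintatolimod control will be considered evaluable for efficacy analysis". The next paragraph puts the Phase IIa primary efficacy analysis on an intention-to-treat population defined by randomization, although Section 19.4 says the trial is not randomized. Neither definition mentions baseline virus.

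**Analysis.** The Phase IIa primary endpoint is the AUC of raw Ct, baseline value included. Section 19.2.2 treats Ct above 40 as right-censored and non-detectable, and says: "A large AUC value for a respective subject is a measure of treatment efficacy as compared to a subject with a lower AUC". The test is one-sided at 0.05 with n=10. Time to a non-detectable Ct is a secondary endpoint.

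**The concern.** The viral-load objective asks whether the regimen changes the course of infection. A patient with no detectable virus before the first infusion cannot show such a change, yet the plan records the most favourable result available. In the time-to-non-detectable analysis the event has already happened at time zero, and the plan does not say how such a patient is handled.

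The bias runs in one direction, toward rejecting the null. No concurrent arm would carry its own share of such patients, so nothing in the design offsets it. Adjusting for baseline Ct would not settle the matter, because these patients are not at risk for the event being timed.

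The plan already applies the principle elsewhere. Section 19.2.2 counts progression to hospitalization only in patients who were not inpatients at entry. The clearance endpoints have no matching restriction.

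**Working it through.** **Inputs.** Section 19.3: baseline Ct mean 24.1, SD 6.5; later SD about 4.5; correlation 0.3, compound symmetry; null AUC 130, alternative 144, n=10, one-sided alpha 0.05, power 0.80. Section 19.2.2: trapezoidal rule. Its text uses Days 0, 3, 7 and 14, while its formula adds Day 30. I use Days 0-14, which Section 19.1 also lists.

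**1. The plan's own power figure.** The Days 0-14 weights are 1.5, 3.5, 5.5 and 3.5. Multiplied by the SDs they give 9.75, 15.75, 24.75 and 15.75, with sum 66 and sum of squares 1203.75.
- Var(AUC) = 0.7 × 1203.75 + 0.3 × 66² = 2149.4, so SD = 46.4 and SE at n=10 = 14.7.
- Power for a difference of 14 is about 0.25 (z) or 0.22 (t). The stated 0.80 is not reproduced; it would need an SD of about 17.8.
- An AUC of 130 over 14 days is a mean Ct of 130/14 = 9.3. A constant Ct of 24.1 already gives 24.1 × 14 = 337.4.

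The benchmark therefore does not fit a 14-day Ct AUC. That is a separate defect. It matters here because a shift on this scale cannot be compared with the planned difference of 14.

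**2. A patient non-detectable throughout.** Each visit contributes at least 40, so the AUC is at least 40 × 14 = 560 (at least 40 × 30 = 1200 if Day 30 is included).

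**3. Effect on the test.** The documents give no post-baseline means, so four profiles were assumed. In each, the null was set to the profile's own AUC (a correctly calibrated benchmark), there was no drug effect, and k of 10 patients were replaced by patients with Ct fixed at its lower bound of 40. Each case used 50,000 simulated trials. The entries are one-sided rejection rates of a one-sample t-test.

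| Assumed mean Ct profile | AUC | Excess of a cleared patient | k=0 | k=1 | k=2 | k=3 |
|---|---|---|---|---|---|---|
| 24.1, 26, 29, 34 (Days 0-14) | 405.65 | 154.35 | 5.0% | 8.8% | 20.5% | 45.2% |
| 24.1, 28, 32, 36 (Days 0-14) | 436.15 | 123.85 | 4.8% | 9.8% | 20.9% | 41.0% |
| Flat 24.1 (Days 0-14) | 337.4 | 222.6 | 5.0% | 5.9% | 19.2% | 51.7% |
| Five equally spaced visits | 130 | 30 | 5.0% | 10.1% | 20.5% | 39.0% |

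One such patient moves the cohort mean by a tenth of the excess but also inflates the sample SD, so the t-test reacts little at k=1. If the SD were treated as known, the rates would be about 17-44%, 43-94% and 76-100% for k=1, 2 and 3. The plan does not say that the SD is known.

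**4. Against the stated null of 130.** On the Days 0-14 profiles the test rejected in every simulated trial, with or without cleared patients. The selection problem affects the AUC test once the benchmark is recalibrated. It affects time to non-detectable whatever the benchmark.

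**The case against.** **Such patients may be rare.** Item 2 asks for symptomatic infection, which reads as current illness. Section 5.1 says "Recruitment efforts will focus on patients with initial signs of COVID-19 who would be offered enrollment as soon as feasible". Section 2.6 reports viral load persisting for several weeks in some immunocompromised patients. If the pilot baseline (24.1, SD 6.5) is taken as normal and representative, P(Ct > 40) is the upper tail beyond (40 − 24.1)/6.5 = 2.45, about 0.7%, or about a 7% chance of at least one such patient in 10. This stands as a reason not to assume a high frequency. It does not close the gap: the recruitment statement is an aim rather than a criterion, symptoms and infiltrates do not establish detectable virus, and the pilot may itself have been selected on positivity.

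**A reader might infer that one cleared patient can produce an effect as large as the one sought.** The documents do not support that. Replacing one of ten patients shifts the Days 0-14 mean by (560 − 337.4)/10 = 22.3 if Ct stays flat at 24.1, 11.1 if it rises linearly to 40 by Day 14 (AUC 448.7), and 5.6 if it reaches 40 by Day 7 (AUC 504.35). Only the flat case exceeds 14, and Section 19.3 says Ct rose after baseline. The 14 also belongs to the 130/144 scale, which does not fit these AUCs. On equally spaced visits, where 130 is plausible, one such patient shifts the mean by 3.

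**A reader might also say that a cleared patient is scored the maximum.** The value is right-censored, so the patient contributes at least 40 per visit rather than an assigned top score. The direction of the bias is the same.

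**Conclusion.** The gap is real. Neither eligibility nor the evaluable rule requires detectable virus before dosing, and the plan's reading of the Ct AUC turns its absence at baseline into evidence of efficacy. The same patients do not belong in the risk set for time to non-detectable.

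The size depends on the number enrolled, which the documents do not give. With no drug effect and a calibrated benchmark, the t-test size goes from 5% to about 6-10% with one such patient, 19-21% with two and 39-52% with three. One is a modest distortion; two or three in ten would undermine the test. These figures rest on the assumed profiles, on Ct fixed at 40 rather than the censored likelihood the plan names, and on a benchmark drawn from patients with detectable baseline virus.

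The documents do not support a claim that such patients will be common, or that this issue alone would decide the result.

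**What to change.** In Section 19.1, replace the randomization-based intention-to-treat sentence, for the viral-load endpoints, with one analysis set for both cohorts. It should comprise treated patients whose last pre-dose nasopharyngeal swab (Day 1, or screening if Day 1 is missing) has a detectable N1 Ct, below 40. Use it for the AUC and for time to non-detectable.

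- **Use N1 alone.** Section 9 names N1 as the analysed variable. Requiring both N1 and N2 below 40 would drop patients who have a measurable value on the endpoint.
- **State how a patient with no pre-dose result is handled.** Section 11.4 allows swabs to be missed for supply reasons. One option is to leave such patients out of this set and keep them in the sensitivity analysis.
- **Apply the same baseline condition to the historical controls.**
- **Keep all treated patients in the safety set**, and report the viral-load analyses on all treated patients as a sensitivity analysis.

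A new entry criterion is not needed. Requiring a positive screening result would constrain same-day dosing when PCR is reported the next day.

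The cost is a short paragraph and no new procedure, since the swab is already scheduled. An occasional treated patient will not count toward the viral-load analysis, which slightly reduces n. The benchmark of 130 needs its own correction.
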